	Q1	Q2	Q3	Q4	Q1	Q2	Q3	Q4	Q1	Q2	Q3	Q4
Study preparation												
IRB approval and renewal												
ClinicalTrials.gov registration												
Develop study instruments and REDCap database												
Adapt CareConekta smartphone app												
Confirm eligibility, recruit and consent participants												
Enrollment questionnaire												
Participant follow-up												
Follow-up questionnaire												
File review												
Data analysis												
Manuscript preparation												
R01 submission and revision												

STUDY DESIGN

Sample Size

We will enroll 200 participants.

For this pilot trial formal sample size estimation was not conducted. The sample size was reached based on the feasible enrolment from the study site within the study timeline. Approximately 4,000 women seek antenatal care at the MOU annually; ~30% of these are HIV-positive, about 1 200 per year, or 100 per month. Our formative work (HREC REF 792/2016 and 227/2017) showed that over half of these women own smartphones. If we conservatively estimate that 30% of all pregnant, HIV-positive women seeking antenatal care each month will be eligible and interested which equals 30 participants enrolled per month. We anticipate that it will take approximately seven months to reach our enrolment target of 200 participants (see Timeline above).

Based on our earlier work in South Africa and at the study site, we estimate that 25% of the participants will engage in long-distance travel during the study period. A sample size of 200 allows us to characterize the mobility experiences of 50 women who travel and explore differences with those who do not. While we do not anticipate having sufficient power to detect statistically significant differences between groups in Aims 2b, the information gained through this pilot study will inform sample sizes for larger future studies should this pilot show promise.

Study arms

- **Control arm (n=100):** Participants will receive standard CareConekta, which will track their mobility and allow the participant to look up new ART facilities upon request.
- **Intervention arm (n=100):** Participants will receive standard CareConekta with the following additions:
 - text notifications of nearby ART facilities when they have traveled >50 km from the study site for >7 days

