 - phone call(s) and/or WhatsApp message(s) from study staff when they have traveled >50 km from the study site for >7 days. The study staff calls and messages will ask about medication supply and will provide assistance with nearby facilities, if requested. The study staff member who conducts interviews will not deliver the intervention calls and/or messages.

STUDY PROCEDURES

This study will consist of two face-to-face study visits as well as abstraction of routine medical records. The details of each visit are described below.

Enrollment visit procedures

Recruitment and assessment of eligibility criteria

Each week during the study recruitment period, study staff will review the list of upcoming appointments at the study site to assess who may be eligible for study participation. Pregnant women attending routine antenatal care services at the Gugulethu Community Health Centre will be approached by trained study recruiters and given brief information about the pilot study. If they are interested, they will be screened to ensure they meet the eligibility criteria using an eligibility checklist. If eligible, they also will be shown a demonstration of CareConekta and its functionality prior to the informed consent process. Text message-level literacy will be demonstrated by reading aloud the text, “I can look up a new clinic on the phone,” in either English or isiXhosa.

Selection of study participants in an equitable manner

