To assess engagement in HIV care, we will report retention in care, which will be assessed at the six-month postpartum point and defined as no documented HIV-specific contact with any healthcare facility (including medication pick-ups) for >3 months. We also will report viral suppression six months after delivery, using thresholds of ≤ 50 and ≤ 1000 copies/ml. Additionally, we will report vertical HIV transmission and completion of the routine 10-week infant PCR test.

We will fit a series of models of mobility metrics on outcomes. For one, we will use a dichotomous exposure of mobility (any travel >50 km: yes/no), we will use Cox proportional hazard regression models to estimate the association of mobility on these outcomes, and will produce adjusted hazard ratios and 95% confidence intervals for retention in care and achieving viral suppression. We also will identify other predictors of engagement in HIV care. We will produce crude Kaplan-Meier curves to time to loss to follow-up and time to viral suppression by mobility group. Additionally, we will perform sensitivity analyses to explore how the estimated effect size changes when using varying cut-off points to define mobility.

Aim 2a. To assess the acceptability and feasibility of the standard and enhanced app, with a focus on identifying user preference and implementation outcomes.

Outcome: Acceptability and feasibility of CareConekta

Acceptability and feasibility data will be collected among all 200 participants. Those in the intervention arm will receive additional questions related to the enhanced app features. The outcomes selected for analysis in Aim 3a correspond with the Technology Acceptance Model for Resource-Limited Settings (TAM-RLS) framework, which was designed to draw attention to end-user acceptability as a predictor of mHealth technology adoption in low-resource settings.⁴⁶ We will report proportions and 95% confidence intervals for categorical variables and medians and interquartile ranges for continuous variables. For open-ended questions, we will create a list of categorical themes that emerge over multiple readings and calculate the proportions for the response categories. We will select key illustrative quotes for each theme.

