Aim 2b. To evaluate the initial efficacy of the enhanced CareConekta intervention, using notifications and staff contact to improve engagement in HIV care, by assessing the association between study arm and engagement in HIV care at six-months postpartum.

Outcome: Efficacy of the intervention

The overall efficacy analysis will include participants in both arms (n=200). To assess overall cohort engagement in HIV care, we will report retention in care, which will be assessed at the six-month postpartum point and defined as no documented HIV-specific contact with any healthcare facility (including medication pick-ups) for >3 months. We also will report viral suppression six months after delivery based on the viral load test closest to the six-month period, using thresholds of ≤50 and ≤1000 copies/ml. Additionally, we will report vertical HIV transmission and completion of the routine 10-week infant PCR test.

Study arm assignment is the primary exposure of interest. We will use Cox proportional hazard regression models to estimate the association of study arm assignment on these outcomes, and will produce adjusted hazard ratios and 95% confidence intervals for retention in care and achieving viral suppression by study arm. We also will identify other predictors of engagement in HIV care. We will produce crude Kaplan-Meier curves to time to loss to follow-up and time to viral suppression by study arm. In a secondary analysis, we will perform an as-treated analysis using self-reported data regarding actually reading the notifications and/or WhatsApp messages or staff phone calls to analyze the effect of receiving the intervention.

HUMAN SUBJECTS' PROTECTION

Ethical review process

The research protocol will be reviewed by the Institutional Review Boards at Vanderbilt University; the University of California, San Francisco; and the University of Cape Town in South Africa. All research activities will occur in South Africa. All procedures will conform to U.S. and South African ethical standards for human subjects' research.

Informed consent

Informed consent will be obtained for all participants as described in the "Informed Consent" section above.

Privacy and confidentiality

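### The Aim 2b as-treated analysis by self-reported reading can show a spurious benefit or harm; report receipt descriptively and add a randomised comparison among app-triggered women

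*Combined protocol and SAP*

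**What the plan says.** The Aim 2b analysis plan states: "Study arm assignment is the primary exposure of interest". Cox models by arm give adjusted hazard ratios for retention and viral suppression. One further sentence adds the secondary analysis: "we will perform an as-treated analysis using self-reported data regarding actually reading the notifications and/or WhatsApp messages or staff phone calls". Its declared purpose is to estimate what receipt does. It names no comparator, time zero, restriction to travellers, or rule for women who give no report.

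Other sections determine who can count as treated:

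- **Study arms.** The intervention arm gets "text notifications of nearby ART facilities when they have traveled >50 km from the study site for >7 days" and "phone call(s) and/or WhatsApp message(s) from study staff when they have traveled >50 km from the study site for >7 days". The control app also tracks mobility.
- **Sample Size.** "we estimate that 25% of the participants will engage in long-distance travel during the study period". The same section says of power: "While we do not anticipate having sufficient power to detect statistically significant differences between groups in Aims 2b".
- **Aim 2a.** "Those in the intervention arm will receive additional questions related to the enhanced app features". The Follow-up questionnaire section places intervention-arm questions at six months.
- **File review activities.** Outcomes are taken from records even for women who do not return for the final visit.
- **Retention.** It is "defined as no documented HIV-specific contact with any healthcare facility (including medication pick-ups) for >3 months". Read literally that describes loss, and I treat it as loss below.

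**The concern.** Three selection steps separate a self-reported reader from the women she would be compared with.

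1. **Travel.** Every exposed woman has crossed the travel threshold. The Introduction presents mobility as a possible barrier to care, and Aim 1b studies it against the same outcomes.
2. **Questionnaire completion.** The reading questions appear to be asked only of the intervention arm and only at six months. This is inferred from the Follow-up questionnaire, schedule of measures and Aim 2a text, since no instrument is shown. A lost woman can therefore have an outcome from files but no exposure report.
3. **Reading.** It is a choice made after randomisation. Control women have nothing equivalent to report, so the would-be readers among them cannot be identified.

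There is also a timing issue. Exposure needs more than 7 days of travel first. If it is coded as fixed from enrolment in a Cox model, the time in care before the message is credited to treatment.

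This is the one analysis meant to isolate the effect of receipt, and the pilot is meant to inform the size of later trials. Disclaiming power does not cover bias.

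**Working it through.** **The plan's own figure.** 200 x 25% = 50 travellers, as stated under Sample Size, so about 25 per arm with 1:1 allocation. I assume that the trigger rate equals the travel rate.

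**Assumptions (no true effect).** Overall loss is 25.2%, a one-year background figure in the Introduction and not a planning value. The remaining rates are not in the documents:

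- risk ratio for loss in travellers (RR): 1.0 to 1.5;
- questionnaire completed by 90% of retained women and a fraction q (60% to 90%) of lost women;
- reading among completers: r_ret if retained, r_lost if lost.

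**Formulas.** Traveller loss is L = RR x 0.252 / (0.75 + 0.25 x RR), which gives 25.2% at RR 1.0 and 33.6% at RR 1.5. Retention among self-reported readers is

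T = (1-L) x 0.9 x r_ret / [(1-L) x 0.9 x r_ret + L x q x r_lost].

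The number of readers n is 25 times the denominator. Retained women overall: 200 x 0.748 = 149.6.

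**Against all other women** (all completing travellers read; women without a report count as untreated). The comparator is (149.6 - nT) / (200 - n).

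- RR 1.5, q 0.9: n = 22.5, T = 66.4%. Comparator (149.6 - 14.94) / 177.5 = 75.9%. Difference -9.5 points.
- RR 1.0, q 0.6: n = 20.61, T = 81.66%. Comparator (149.6 - 16.83) / 179.39 = 74.01%. Difference +7.6 points (7.648 before rounding).

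**Against all control-arm travellers, intervention women without a report dropped.** RR 1.5, q 0.6: 74.8% v 66.4% = +8.4. With q 0.9 the difference is 0.

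**Against control-arm travellers who completed the questionnaire.**

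| Reading, retained / lost | RR 1.0, q 0.6 | RR 1.5, q 0.9 |
|---|---|---|
| 90% / 60% | 87.0% v 81.7% = +5.3 | 74.8% v 66.4% = +8.4 |
| 90% / 75% | 84.2% v 81.7% = +2.6 | 70.3% v 66.4% = +3.9 |
| 70% / 70% | 0 | 0 |

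Differences are taken before rounding. When r_ret = r_lost the two terms cancel, so the bias is zero whatever the reading rate. If completion among lost women differs by arm (60% intervention, 50% control; all completers read), the bias is -2.6 (RR 1.0) to -3.3 (RR 1.5).

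**Timing alone.** I take a simulation with constant hazard, 25.2% loss by nine months, first trigger uniform over months 0-9 or 3-6, and exposure fixed from enrolment. The hazard ratio for loss against control-arm travellers depends on the share of women already out of care who are still triggered and read. It is 0.47 to 0.50 if none are, about 0.75 if half are, and 1.0 if all are. With the trigger as time zero, comparing arms among women in care at that point, it is 0.99 to 1.00.

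**Precision of randomised arms among triggered women.** The 95% half-width is 1.96 x sqrt(2p(1-p)/25). For p = 0.252, 0.336 and 0.479 (the last is the Introduction's other loss figure) it is 24.1, 26.2 and 27.7 points. The as-treated contrast against travelling control completers has about 23 to 30 points.

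**The case against.** The analysis is secondary, arm assignment is primary, and the protocol says that it does not expect adequate power for Aim 2b. Completion, reading and traveller risk are assumed here. The plan makes at least three contact attempts, by phone or home visit, and allows the questionnaire by telephone, so completion may depend only weakly on retention in care. All of this stands, and it limits the weight of the point.

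Some stronger readings are tempting but not supported:

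- **That no comparator could ever work.** Against travelling control completers the bias is zero if reading is unrelated to retention and completion is similar by arm. The documents do not quantify either.
- **That immortal time would roughly halve the hazard ratio.** That needs no woman already out of care to be triggered and read. The trigger depends on location and not on care status. The plan also does not say that the as-treated analysis is a Cox model from enrolment, although Cox is the method named for Aim 2b.
- **That women triggered late should be excluded because a gap of more than 3 months could no longer develop.** A gap runs from the last contact. A woman last seen two months before a trigger that falls two months before assessment has a four-month gap, and the message could have closed it.
- **That a comparison of triggered women answers the receipt question.** It estimates the effect of assignment at the trigger.

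**Conclusion.** The concern holds in a limited form. As written, the as-treated contrast can give a spurious result of either sign, because the comparator, the time zero and the handling of missing reports are open. The illustrative range is about -9.5 to +7.6 retention points against all other women. Against travelling control completers it is about +2.6 to +8.4 if reading is related to retention, and 0 if it is not. The mechanisms come from the documents, apart from the inferred placement of the reading questions. The sizes rest on the assumed rates. At 47.9% loss, the 90% / 60% reading case gives +9.0 to +10.1.

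Immortal-time bias is possible, but its size cannot be fixed from the documents. A reader might infer that the trial's efficacy conclusion is compromised. It is not, because the primary Aim 2b comparison uses all randomised women by arm. A proportionate response is a change to one secondary analysis.

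**What to change.** 1. Report self-reported reading and the staff contact log as a description of receipt. Alternatively, keep the as-treated contrast as exploratory only, and do not present it as an estimate of what receipt does.
2. Add an exploratory comparison of arms as randomised among all women in both arms whose app recorded a first trigger (>50 km, >7 days), with outcomes from file review. Keep late triggers in, and report by time from trigger to assessment as a sensitivity analysis. Use the trigger date as time zero in any time-to-event model.
3. State that this estimates the effect of assignment at the trigger. An effect of receipt would need a randomisation-based complier estimate, with an exclusion restriction and a sound measure of receipt. For example, if 68% of triggered women read and reading adds 20 points, the arms differ by 0.68 x 20 = 13.6, and 13.6 / 0.68 returns 20.
4. Report app installation, GPS completeness and trigger frequency by arm. Installation follows randomisation, so the comparison is protected only if detection is similar. As an example, at 33.6% loss, detecting 90% of retained and 80% of lost women in one arm against 80% and 60% in the other gives -3.5 points.
5. Reconcile About CareConekta, which describes the automatic travel notification without limiting it to an arm, with Study arms and Interim procedures, which place it in the intervention arm. The comparison depends on the answer.

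**Cost.** Analysis-plan wording and some programming; mobility is already tracked in both arms and contact attempts are already logged. The downside is width: at about 25 women per arm this is an estimate and not a test, and it is not clearly more precise than the as-treated contrast. Its advantage is less bias. One limit remains: visit and dispensing records cover only the Western Cape, while laboratory records are national, so care taken up elsewhere may be missed. The all-randomised comparison (n=200) stays primary.

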After the enrollment questionnaire, the participant will be invited to install the app on her own phone, with assistance available from study staff. The app will be provided free of charge. The participant will enter her phone number into the app during installation, which will be automatically confirmed through a one-time PIN.

Reimbursement

After all the above steps are complete, the enrollment visit will conclude with providing the participant R150 reimbursement for transport and missed opportunity costs. Payment will be made in cash and/or grocery vouchers and will be recorded in a reimbursement log. Data charges to

compensate for data used by the app will be reverse-billed to the study and will not be the responsibility of participants.

Interim procedures

Interim procedures for participants in the intervention arm

Participants in the intervention arm will receive text notifications of nearby ART facilities when they have traveled >50 km from the study site for >7 days. They also will receive phone call(s) and/or WhatsApp messages from study staff to when they have met this travel threshold. The study staff calls and messages will provide adherence support and assistance with connecting to nearby facilities, if requested. Messages will be written at an 8th-grade reading level or lower. All contact attempts (successful or not) will be recorded on a contact log.

Other notifications

Participants in both arms may receive notifications via the CareConekta app that are unrelated to linkage to ART care and nearby health facilities. Such notifications may include reminders to keep the app installed on the phone or messages about the raffle incentive (see below). There is no charge to the participant for receiving notifications.

Follow-up phone call

We will contact all participants by phone approximately one week after the expected delivery date to determine current location, and infant name and date of birth. This contact may take place in person at the study site if the participant is attending a regularly scheduled visit. We are including this step due the difficulty of tracing infant outcomes and linking mother-child dyads without infant date of birth and name. This information will be recorded on a CRF and captured in REDCap. A minimum of three contact attempts will be made for each participant. All contact attempts (successful or not) will be recorded on a contact log.

Mobility data

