Electronic and paper files will be reviewed after the participant's final visit to assess engagement in HIV care. If the participant fails to return for a final visit, files will be reviewed a minimum of seven months after estimated delivery. Electronic data on health facility visits and pharmacy dispensing, including facility recorded deaths, will be requested the Provincial Health Data Centre of the Western Cape Department of Health by providing a list of folder numbers of women who have consented and enrolled in the study. These data include all public health facilities in the Western Cape Province, which is the location of the study site. Laboratory records, including viral loads, from any South African facility will be abstracted from the NHLS database. Participants in both arms who are lost from the study at the time of study close will be traced through staff outreach and electronic/paper medical records. Informed consent will include permission to link with electronic medical records.

Table of schedule of measures

Item for completion	Enrolment	Early postpartum phone call	6 months postpartum
Eligibility Checklist	x		
Informed Consent	x		
Linkage form	x	x child details	
Randomisation log	x		
Demographics and medical history	x		x
Maternal mobility (past and planned)	x		x
Maternal clinic switching	x		x
Perceived barriers and facilitators of engagement in care	x		x
Depression (PHQ-4)	x		x
Alcohol and drug use (AUDIT-C and DUDIT Q1)	x		x
Patient provider relationship scale	x		x
ART adherence	x		x
WHO VAW (intimate partner violence)	x		
Social impact scale (stigma)	x		
Availability of social support	x		
Life events (trauma)			x
Infant health			x
Child mobility			x
Acceptability of CareConekta			x
Impact of COVID-19 & lockdown of HIV care and mobility			x
Laboratory tests			
HIV viral load*			x
Record review			
Antenatal and obstetric information	x	x	x
ART pharmacy records	x	x	x
Maternal laboratory results	x	x	x
Child HIV testing		x	x

* If no routine viral load result found in the three months before the study visit

DATA COLLECTION AND STORAGE

Data collection methods

Data will be collected in three ways:

- Face-to-face enrollment and follow-up questionnaires

- Medical record review (electronic and paper file records) to determine participant engagement in HIV care
- Electronic app usage and mobility data

Questionnaire data

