The PI will monitor the study safety data on an ongoing basis. They will report to their IRBs and the South Africa HREC any breaches in confidentiality identified. In the event that a breach in confidentiality does occur, staff will be retrained on human subjects' protection and confidentiality if possible or removed from subject contact if the either the breach is too serious or if the PIs feel the staff member cannot be sufficiently retrained. Staff will be made aware of this condition on employment.

The PI will be responsible for reporting to the grant program director any action resulting in a temporary or permanent suspension of the research.

We will not convene a Data Safety Monitoring Board (DSMB) for this study.

Data accuracy and completeness

In addition to the co-investigators, the local South African study team will consist of a study coordinator, a site coordinator, and an interviewer/fieldworker. These team members will be trained in human subjects' research through the NIH's website or through a presentation developed by UCT faculty based on the NIH course, but adapted to the local context. Prior to contact with any subjects, all staff with participant interaction duties will be trained on the background and objectives of the study, procedures for obtaining informed consent, and correct administration of the questionnaire. Training will include procedures for minimizing risk to subjects, assuring data accuracy and protocol

compliance. The study team will also be asked to complete several practice interviews. To avoid bias and/or contamination, the study staff member who conducts interviews will not deliver the intervention calls and/or messages.

Participant remuneration

Following standards set by the University of Cape Town Research Ethics Committee, all participants will be reimbursed R150 (approximately US \$10.50) per study visit (enrollment and follow-up) for transport and missed opportunity costs. There will be no participant reimbursement for routine care visits made between study visits.

REFERENCES

1. Statistics South Africa. *Mid-Year Population Estimates 2018*. Pretoria; 2018. <https://www.statssa.gov.za/publications/P0302/P03022018.pdf>.
2. UNAIDS. *Global Report: UNAIDS Report on the Global AIDS Epidemic 2013*. Geneva; 2013. http://www.unaids.org/en/media/unaids/contentassets/documents/epidemiology/2013/gr2013/UNAIDS_Global_Report_2013_en.pdf.

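### No masking or caller separation is stated for the file review and tracing that determine retention, so care outside the Western Cape could be found more completely in the intervention arm

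*Combined protocol and SAP*

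**What the plan says.** The separation rule appears twice, with the same scope: once under Study arms, and once under Data accuracy and completeness, which adds its purpose: "To avoid bias and/or contamination, the study staff member who conducts interviews will not deliver the intervention calls and/or messages".

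For Aim 2b, the retention definition turns on "no documented HIV-specific contact with any healthcare facility (including medication pick-ups) for >3 months". (Those words describe loss; retention is its absence.) The source is given under File review activities: "Electronic and paper files will be reviewed after the participant's final visit to assess engagement in HIV care". Women in both arms who are lost at study close "will be traced through staff outreach and electronic/paper medical records". That section names no reviewer or tracer, states no masking, and does not say whether the intervention contact log may be consulted.

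The same section limits the electronic visit and dispensing data to public facilities in the Western Cape. Laboratory records come from the national database and cover any South African facility.

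In the intervention arm only, staff contact women who pass the travel threshold, ask about medication supply and offer "assistance with connecting to nearby facilities, if requested". Every contact attempt is logged (Study arms; Interim procedures for participants in the intervention arm).

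**The concern.** The retention definition counts contact with any facility, but the visit and dispensing data stop at the provincial border. The Study site section says women often travel between this clinic and the Eastern Cape, and the Introduction says that unrecognised transfers between facilities make programme effectiveness hard to assess. Once a woman has left the province, a clinic visit or medication pick-up that leaves no laboratory record can be documented only through tracing or paper files.

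Staff who helped an intervention woman reach a clinic may know where to look for her. If the same staff review files or trace, or if their knowledge is passed on, her contact is more likely to be documented than that of a control woman who did the same thing unaided. Equal incompleteness in both arms would blur the comparison. Unequal incompleteness would shift it in favour of the intervention, and in the travellers, where any true effect has to arise. Low power does not remove the problem, because the Sample Size section intends the results to inform the size of later trials.

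**Working it through.** **1. The plan's own figure.** Sample Size expects 25% of participants to travel long distance: 200 × 0.25 = 50, as stated. With 1:1 allocation that is about 25 per arm.

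**2. Where unequal detection can act.**
- Moves within the Western Cape: found from the provincial extract, requested by a list of folder numbers. Arm-neutral.
- Care anywhere that leaves a laboratory record: found from the national database. Arm-neutral.
- Care outside the province with no laboratory record: found only by tracing or paper files. This is the exposed group.
- Viral suppression: Aim 2b defines it as "viral suppression six months after delivery based on the viral load test closest to the six-month period". The result comes from the national database or a study blood draw, so it depends far less on knowing which clinic a woman uses.

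**3. Leads available to a tracer.**
- Both arms: GPS, sent as a random point within 1 km of the true position, which gives an area and not a clinic; a call about one week after the expected delivery date, roughly six months before the outcome; alternative contacts; and clinic-switching questions at six months, answered only by women who are reached.
- Intervention arm only: whatever staff learn during help calls.

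**4. Size if the path operates.** Assume no true effect. The spurious difference in retention is

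d = t × r × o × g

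- t = 0.25, the share who travel (Sample Size).
- r = true retention = 1 − loss. Two loss rates from the Introduction serve as scenarios: 25.2% at one year among women pregnant at ART initiation, and 47.9% within six months of delivery among women diagnosed in antenatal care in Johannesburg. So r = 0.748 or 0.521.
- o = share of retained travellers whose contacts can be found only by tracing. Assumption; the plan gives no figure.
- g = excess probability of finding those contacts in the intervention arm. Assumption; the plan gives no figure.

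With o = g = 0.5:
- r = 0.748: d = 0.25 × 0.748 × 0.5 × 0.5 = 0.047, or 4.7 points (65.4% against 70.1%).
- r = 0.521: d = 0.25 × 0.521 × 0.5 × 0.5 = 0.033, or 3.3 points (45.6% against 48.8%).

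The percentages set control-arm detection of these contacts to zero; d itself depends only on the gap g. With 100 per arm and a two-sided 5% test of two proportions, the chance of a significant result favouring the intervention is 10.5% and 6.7%, against a nominal 2.5%. The planned analysis is Cox regression, so this test is a simplification.

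Across o and g from 0.25 to 1, d runs from 0.8 to 18.7 points; the top (o = g = 1) is an extreme bound. With g = 0, d = 0.

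**5. Scale.** If travellers were lost at those average rates and the intervention kept every one in care, the true gain would be 25 × 0.252 = 6.3 points or 25 × 0.479 = 12.0 points. The standard error of a difference at an assumed 70% retention is √(2 × 0.7 × 0.3 / 100) = 0.065, or 6.5 points.

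**The case against.** A reader might infer that staff have leads in the intervention arm only. The documents do not support that. Tracing is planned for both arms, the control app also tracks mobility, every participant is due the postpartum call, and at six months every woman gets at least three contact attempts and a questionnaire that may be done by telephone. What remains is a possible difference in how specific the leads are, mostly for women not reached at six months.

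A reader might also infer that the calls are known to record each woman's clinic. They are not. Help is given on request, the log is described as recording contact attempts, and nothing says that call information reaches whoever reviews files. Nor does the plan say that paper files at clinics outside the province will be obtained; if they are not, and outreach does not document the contact either, a clinic name adds nothing. This stands, and it is why zero belongs in the range.

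That the same person would call and trace is likewise an inference. The local team has three roles, the interviewer may not call, and the study coordinator has access to the allocation envelopes, so overlap is plausible; the plan does not assign the tasks.

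Finally, this is a pilot that disclaims power for Aim 2b, and 3.3 to 4.7 points is less than one standard error. That is true, but sampling error averages out over repetitions and differential ascertainment does not.

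**Conclusion.** The gap in the rule is real: it separates the interviewer from delivery and leaves the steps that determine retention with no stated masking or separation. The resulting bias is possible, not demonstrated. It is confined to women who leave the Western Cape and whose care leaves no laboratory record, and it bears on retention; reading it as a flaw in the whole efficacy analysis would go too far, since viral suppression is little exposed.

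The size is unknown. It is zero if call information is not used, and a few percentage points if half of retained travellers can be found only by tracing and the detection gap is 50 points. Both values are assumptions. The artefact should not be quoted as a fixed fraction of the largest achievable effect: the 6.3 and 12.0 points rest on average loss rates borrowed from other groups, and if every traveller would otherwise be lost the ceiling would be 25 points. The plan should close the path, because it lies in the subgroup the intervention targets and closing it is cheap.

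**What to change.** Extend the separation rule to File review activities.

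- Code primary retention in both arms by a fixed script from the provincial and national laboratory extracts, before arm is merged.
- Have paper-file abstraction and tracing done by existing staff who did not make the calls, without the intervention contact log, and with the same sources and steps in both arms.
- Report retention with and without contacts known only through intervention calls.

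The cost is a short protocol addition and some reassignment of tasks; no extra staff are needed. There are two drawbacks. Some true contacts known only from calls drop out of the main analysis, which can hide genuine linkage to care, so both versions need to be shown. And in a three-role team the tracer may not be fully masked: the study coordinator has access to the allocation envelopes, and the interviewer puts additional questions to intervention women at six months. Scripted coding from the extracts protects the primary result even where masking of the tracer is incomplete.
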